6.1.3. Lost to Follow-up

A subject who repeatedly fails to return for scheduled visits and is unable to be contacted by the study site will be considered lost to follow-up.

The following actions should be taken if a subject fails to return to the clinic for a required study visit:

- Attempt to contact the subject and reschedule the missed visit as soon as possible and counsel the subject on the importance of maintaining the assigned visit schedule and determine whether or not the subject wishes to and/or should continue in the study.
- Before a subject is deemed lost to follow-up, the investigator or designee must make every effort to contact the subject. These contact attempts should be documented in the subject's medical record.

7. STUDY ASSESSMENT AND PROCEDURES

7.1. Assessment of Efficacy

Response assessments will be performed by radiological imaging using RECIST 1.1 criteria every 6 weeks (±7 days) until disease progression. After Cycle 8, scans may be performed every 9 weeks. If any subject responds with a CR or PR at any assessment, then the subsequent confirmatory scan should be performed 4 weeks (+5 days) after the previous scan where the objective response was first evidenced. Assessment of response and the primary endpoint, PFS, will be assessed by an independent central reader who will be blinded to treatment assignment.

Subjects should be followed with the same imaging procedure throughout the study. Computed tomography scans or magnetic resonance imaging may be used as clinically indicated. If the subject withdraws for reasons other than tumor progression, an EOT scan should be performed if the last scan was \geq 3 weeks earlier.

Survival follow-up will continue by phone every 3 months until the later of 184 events or 2 years after the last subject is randomized.

7.2. Assessment of Safety

7.2.1. Safety Parameters

Subjects will be monitored closely for AEs and laboratory abnormalities during the study. All AEs that occur after any subject has been enrolled, before treatment, during treatment, or within 30 days following the cessation of treatment, whether or not they are related to the study, must be recorded on forms provided by PTC.

For AEs and laboratory abnormalities, the investigator should use his/her judgment in determining whether the event or abnormality is clinically significant, whether diagnostic evaluation is warranted, and whether potential interruption of study drug therapy is appropriate. In general, life-threatening (Grade 4) or severe (Grade 3) AEs or laboratory abnormalities should be considered clinically significant, although recurrent or persistent moderate events (Grade 2) may also be considered clinically significant in certain circumstances. Reference should be made to the NCI Common Terminology Criteria for Adverse Events Version 5.0 (CTCAE V5.0) for grading the severity of AEs and laboratory abnormalities.

While specific monitoring, diagnostic testing, and supportive care measures must be instituted based on the clinical judgment of the investigator, investigators should contact the PTC Medical Monitor to obtain guidance and to ascertain whether similar events are being seen at other sites. The PTC Medical Monitor should be notified of any AE or laboratory abnormality that leads to dose interruption and should be apprised of ancillary laboratory or other diagnostic findings and the evolving data from any work-up of the initial abnormality. The PTC Medical Monitor may suggest review of the case with consultants or with other experts (either at the site or retained by PTC).

Additional safety assessments include vital signs, ECGs, physical examinations, and ECOG PS scores.

7.3. Adverse Events and Serious Adverse Events

7.3.1. Definition of Adverse Event

An AE is any untoward medical occurrence after exposure to a drug in humans, whether or not it is considered related to the drug. An AE can therefore be any unfavorable or unintended sign (including an abnormal laboratory finding), symptom, or disease in a study subject who is administered study drug in this study.

For this protocol, untoward medical occurrences that should be reported as AEs include the following:

- All AEs during treatment with study drug administration
- All AEs resulting from medication misuse, abuse, withdrawal, or overdose of study drug
- All AEs resulting from medication errors such as dispensing or administration error outside of what is described in the protocol
- Apparently unrelated illnesses, including worsening of a preexisting illness
- Injury or accidents. Note that if a medical condition is known to have caused the injury or accident (a fall secondary to dizziness), the medical condition (dizziness) and the accident (fall) should be reported as 2 separate AEs. The outcome of the accident (hip fracture secondary to the fall) should be recorded in source documents.
- Abnormalities in physiological testing or physical examination findings that require clinical intervention or further investigation (beyond ordering a repeat [confirmatory] test)
- Laboratory or ECG abnormalities that require clinical intervention or further investigation (beyond ordering a repeat [confirmatory] test) unless they are associated with an already reported clinical event. Laboratory abnormalities associated with a clinical event should be captured in the source documents. Laboratory abnormalities not requiring clinical intervention or further investigation will be captured as part of overall laboratory monitoring and should not be reported as AEs.
- A preexisting condition (eg, allergic rhinitis) must be noted on the appropriate eCRF but should not be reported as an AE unless the condition worsens, or episodes increase in frequency during the AE reporting period.
- Diagnostic and therapeutic noninvasive and invasive procedures, such as surgery, should not be reported as AEs. However, the medical condition for which the procedure was performed should be reported if it meets the definition of an AE. For example, an acute appendicitis that occurs during the treatment with study drug should be reported as the AE and the resulting appendectomy should be recorded in the source documents and eCRF. If a surgical procedure was planned before entry into the study, and the surgery is not performed because of a worsening of a baseline condition, this should not be reported as an AE. Note that, as described in Section 7.3.2, any hospitalization occurring as the consequence of an AE during the study period should be reported as an SAE.

Each AE is to be classified as serious or nonserious by the investigator using medical and scientific judgment.

7.3.2. Definition of Serious Adverse Events

An SAE is an untoward medical occurrence or effect that occurs after exposure to a study drug at any dose, regardless of whether it is considered to be related to the study drug, which results in one of the following:

- Results in death. This includes all deaths on treatment or within 30 days after last study drug administration, including deaths due to disease progression. Any death occurring later than 30 days following the last dose need not be reported as an SAE unless it is a result of an event that started within the period covered by the on-study definition. The reported AE should be the event that caused the death. In addition, any AE resulting in death that occurs subsequent to the AE reporting period and that the investigator assesses as possibly related to the study drug should also be reported as serious.
- Is life-threatening. This refers to an event in which the subject was at risk of death at the time of the event. It does not include an event that, had it occurred in a more severe form, hypothetically might have caused death.
- Requires hospitalization or prolongation of existing hospitalization (excluding hospitalizations for administration of the study drug, procedures required by the study protocol, or treatment-related diagnostic procedures; other planned hospitalizations; or hospitalizations related only to progression of disease).
- Medical and scientific judgment should be exercised in deciding whether expedited reporting is appropriate in other situations, such as important medical events that may not be immediately life-threatening or result in death or hospitalization but may jeopardize the subject or may require intervention to prevent one of the other outcomes listed in the definition above. These should also usually be considered serious. Examples of such events are intensive treatment in an emergency room or at home for allergic bronchospasm, blood dyscrasias or convulsions that do not result in hospitalization, or development of drug dependency or drug abuse.
- Additionally, hospitalization should be used as an indicator of the seriousness of the AE and should only be used for situations where the AE truly fits this definition and not for hospitalizations associated with less serious events (eg, a hospital visit where subject is admitted for observation or minor treatment [eg, hydration] and released in less than 24 hours). Furthermore, hospitalization for PK sampling, if needed, is not an AE.
- Results in persistent or significant disability or incapacity or substantial disruption of the ability to conduct normal life functions, not related to cancer.
- Any other medically important event that the investigator or PTC judges to be serious or which is defined as serious by the regulatory agency in the local country. These are AEs that might not be immediately life-threatening or result in death or hospitalization but might jeopardize the subject or might require intervention to prevent one of the other outcomes listed above. Medical judgment should be

exercised in deciding whether an AE is serious based on above definition. Examples of such events are intensive treatment in an emergency room or at home for allergic bronchospasm, blood dyscrasias or convulsions that do not result in hospitalization, or development of drug dependency or drug abuse.

• A pregnancy resulting in spontaneous abortion, stillbirth, neonatal death, or congenital anomaly (including that in an aborted fetus).

Note that any SAEs occurring from signing of consent form through 30 days after the end of the subject's participation in the study (last dose) should be reported to PTC if the investigator becomes aware of them.

7.3.2.1. Disease Progression

An event need not be reported as an SAE if it exclusively represents a relapse or an expected change or progression of the baseline cancer. In case of fatal outcome with disease progression, it should be reported in "Results in death" subsection (refer to Section 7.3.2).

7.3.3. Unexpected Adverse Events

The Reference Safety Information (RSI) will be used for assessing expectedness. The RSI for the purpose of expedited safety reporting for unesbulin is located in Section 7 of the Unesbulin IB. The RSI for DTIC may be found in local dacarbazine Product Information or Summary of Product Characteristics.

If an event is not listed in the RSI, it should be considered unexpected, or if the AE occurs at a greater severity, specificity, or frequency, it should be considered unexpected.

7.3.4. Eliciting Adverse Event Information

The investigator is to report all directly observed AEs and all AEs spontaneously reported by the subject. In addition, each study subject will be questioned about AEs at each scheduled clinic visit after study drug administration or during any telephone contact with the subject. The type of question asked should be open-ended, for example, "How have you been feeling?" or a similar type of query.

7.3.5. Recording Nonserious Adverse Events

All AEs (both serious and nonserious) that occur in subjects during the AE reporting period must be recorded, whether or not the event is considered drug related. In addition, any untoward event that occurs subsequent to the AE reporting period that the investigator assesses as possibly related to the investigational drug/product should also be recorded as an AE.

All AEs are to be recorded in the source documents and on the eCRF using concise medical terminology; whenever possible, terms contained in the Medical Dictionary for Regulatory Activities (MedDRA) should be employed. In addition, the following information should be recorded:

- Indication of whether the event is nonserious or serious (see Section 7.3.1 and Section 7.3.2, respectively)
- Relationship to study drug (see Section 7.3.6)

- Severity of the event (see Section 7.3.7)
- Onset date
- Date of resolution or date of death
- Action taken
- Outcome of the event
- Whether the AE resulted in discontinuation from the study or treatment

Classification of the event as serious or nonserious determines the reporting procedures to be followed.

7.3.6. Describing Adverse Event Relationship to Study Drug

The investigator should provide an assessment of the relationship of the AE to the study drug (ie, whether there is a reasonable possibility that the study drug caused the AE) using the considerations outlined in Table 4.

Relationship Category	Description
Probable	A clinical event in which a relationship to the study drug seems probable because of such factors as consistency with known effects of the drug; a clear temporal association with the use of the drug; improvement upon withdrawal of the drug; recurrence upon rechallenge with the drug; lack of alternative explanations for the event.
Possible	A clinical event occurring coincident with administration of the study drug and which may or may not be explained by concurrent disease or other drugs or chemicals. Information on drug withdrawal or rechallenge may be lacking.
Unlikely	A clinical event with a temporal relationship to the study drug exposure that does not preclude causality but for which there is a clear alternate cause that is more likely to have caused the adverse event than study drug. Such alternatives include a concomitantly administered drug, the subject's disease state, other medical conditions, or environmental factors.
Unrelated	A clinical event, for which a relationship to the study drug seems improbable because of factors such as inconsistency with known effects of the study drug, lack of a temporal association with study drug administration, lack of association of the event with study drug withdrawal or rechallenge, and/or presence of alternative explanations for the event. Alternative explanations might include a known relationship of the adverse event to a concomitant drug, medical history of a similar event, the subject's disease state, other medical conditions, or environmental factors.

Table 4:	Relationship of Study Drug to Adverse Event
----------	---

7.3.7. Grading of Severity of Adverse Event

The severity of AE will be graded using the latest version of the NCI CTCAE V5.0 (refer to Study Manual). For each episode, the highest severity grade attained should be reported.

If an NCI CTCAE V5.0 criterion does not exist, the investigator should use the grade or adjectives: Grade 1 (mild), Grade 2 (moderate), Grade 3 (severe), Grade 4 (life-threatening), or Grade 5 (fatal) to describe the maximum intensity of the AE. For purposes of consistency with the NCI CTCAE V5.0, these intensity grades are defined in Table 5.

Grade	Severity Grade	Description
1	Mild	Sign or symptom is present, but it is easily tolerated, is not expected to have a clinically significant effect on the subject's overall health and well-being, does not interfere with the subject's usual function, and is not likely to require medical attention
2	Moderate	Sign or symptom causes interference with usual activity or affects clinical status, and may require medical intervention
3	Severe	Sign or symptom is incapacitating or significantly affects clinical status and likely requires medical intervention and/or close follow-up
4	Life-threatening	Sign or symptom results in a potential threat to life
5	Fatal	Sign or symptom results in death

Table 5: Grading of Adverse Events

7.3.8. Reporting Adverse Events

Investigator site reporting requirements for AEs are summarized in Table 6.

Event	Recorded in the	Reported on the SAE Report Form to PTC
	eCRF	Pharmacovigilance Within 24 Hours of Awareness
Serious AE	All	All
Nonserious AE	All	None
Exposure to the study drug during pregnancy or breastfeeding, and occupational	All (regardless of whether associated with an AE), except occupational exposure	Exposure during pregnancy, exposure via breastfeeding, occupational exposure (regardless of whether associated with an AE)

 Table 6:
 Investigator Site Requirements for Reporting Adverse Events

Abbreviations: AE, adverse event; eCRF, electronic case report form; SAE, serious adverse event

All AEs should be followed up by the investigator until they are resolved, or the investigator assesses them as chronic or stable. The investigator should consider protocol guidelines and use his/her discretion in ordering additional tests as necessary to monitor the resolution of such events. In the event of additional investigations, the PTC Pharmacovigilance Department or designee should be informed via email or fax. A subject withdrawn from the study because of an AE must be followed by the investigator until clinical recovery is complete and laboratory results have returned to normal, or until progression has been stabilized. Follow-up may need to continue after the subject has discontinued from the study, and additional investigations may be requested by the PTC Medical Monitoring team.

The first day of AE reporting will coincide with the date of signing of the informed consent form (ICF) and will include a minimum of 30 calendar days after the last administration of study drug.

7.3.9. Serious Adverse Events Reporting

All SAEs occurring from the signing of the ICF through 30 days after the end of the subject's participation in the study (last dose) should be reported via the SAE report form to PTC immediately but no later than 24 hours of becoming aware of the event(s). In addition, the AE portion of the eCRF must also be completed.

exposure

The SAE report form should be signed by the investigator; however, if the investigator is unable to sign at the time of the event or within 24 hours, the form should be signed by the clinical staff member reporting the SAE (eg, the study coordinator). The SAE report form must be faxed or emailed to the PTC Pharmacovigilance Department or designee and to the site Institutional Review Board (IRB) or Institutional Ethics Committee (IEC) (if required by local regulations) within 24 hours.

Follow-up information to the SAE should be clearly documented as "follow-up" in the SAE report form and must also be faxed or emailed to the same party. All follow-up SAE report forms for the event must be signed by the investigator. Any source documents (eg, progress notes, nurses' notes, laboratory and diagnostic test results, discharge summaries) provided to PTC should be redacted so that the subject's name, address, and other personal identity information are obscured. Only the subject's study number and initials are to be provided (in regions where the provision of such information is permitted). The information in the AE portion of the eCRF and the SAE report form(s) must match or be reconciled. Where the same data are collected, the forms must be completed in a consistent manner. For example, the same AE term should be used on both forms.

In the rare event that the investigator does not become aware of the occurrence of an SAE immediately (for example, if a subject initially seeks treatment elsewhere), the investigator is to report the event within 24 hours after learning of it and to document his/her first awareness of the AE.

The PTC Pharmacovigilance Department contact information for reporting SAEs is provided below. This information is also provided in the SAE report form.

PTC Therapeutics Safety Department Attention: Pharmacovigilance Email: [contact] Facsimile (USA): [contact]

7.3.10. Contraception

For pregnancy testing and contraception requirements in WOCBP and contraception requirements and sperm donation limitations in males who are sexually active with WOCBP, see the corresponding inclusion criteria in Section 4.1.

7.3.11. Reporting Pregnancy

PTC should be notified if a female subject in the study, or a female partner of a male subject in the study, becomes pregnant on study or within 30 days of the last administration of study drug. The pregnancy must be reported on a Pregnancy Notification Form (see Study Manual for details).

This must be done whether or not an AE has occurred and within 24 hours of awareness of the pregnancy. The information submitted should include the anticipated date of birth or pregnancy termination.

Written consent is required before collecting and reporting any information on a female partner of a male subject in the study.

If possible, the investigator should follow the subject, or the pregnant female partner of a male subject, until completion of the pregnancy and notify the PTC Medical Monitor of the outcome within 5 days or as specified below. The investigator will provide this information as a follow-up to the initial Pregnancy Notification Form via the Pregnancy Outcome Form (see Study Manual for details).

If the outcome of the pregnancy meets the criteria for immediate classification as an SAE (ie, spontaneous abortion, stillbirth, neonatal death, or congenital anomaly [including that in an aborted fetus]), the investigator should follow the procedures for reporting SAEs, ie, report the event to the PTC Pharmacovigilance Department or designee and follow up by submission of appropriate AE eCRFs (see Section 7.3.9).

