- 19. Women of childbearing potential (WOCBP; as defined by the Clinical Trials Facilitation and Coordination Group [CTFG]) must have a negative serum pregnancy test at screening and agree to abstinence or the use of at least one of the following highly effective forms of contraception (with a failure rate of <1% per year when used consistently and correctly) (Clinical Trials Facilitation and Coordination Group 2020). Contraception or abstinence must be continued for the duration of the study and for at least 6 months after the last dose of study drug:

 - Combined (estrogen and progestogen containing) hormonal contraception associated with inhibition of ovulation:
 - Oral
 - Intravaginal
 - Transdermal
 - Progestogen-only hormonal contraception associated with inhibition of ovulation:
 - Oral
 - Injectable
 - Implantable
 - Intrauterine device
 - Intrauterine hormone-releasing system

- Bilateral tubal occlusion
- Vasectomized partner with confirmed azoospermia

All females will be considered of childbearing potential unless they are postmenopausal (at least 12 months consecutive amenorrhea in the appropriate age group without other known or suspected cause) or have been sterilized surgically (eg, bilateral salpingectomy, hysterectomy, bilateral oophorectomy).

- 20. Lactating females are not eligible unless they have agreed not to breastfeed their infants during treatment and for a period of 1 month following completion of treatment.
- 21. Males who are sexually active with WOCBP and who have not had a vasectomy must agree to use a barrier method of birth control from the start of study drug administration through at least 6 months after the last dose of study drug. Males should not donate sperm from the start of study treatment through at least 6 months after the last dose of study drug.

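### The required pregnancy-notification window (on study or within 30 days of the last dose) is shorter than the protocol's own 6-month post-dose contraception period, and 'on study' is not defined

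*Protocol*

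**What the plan says.** Section 7.3.11 sets the notification rule. The sponsor is to be told, on a Pregnancy Notification Form and within 24 hours of the site learning of it, if a female subject or a male subject's female partner "becomes pregnant on study or within 30 days of the last administration of study drug". The pregnancy is then followed to its outcome where possible.

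Section 4.1 sets the contraception rule; the Synopsis gives the same periods. Criterion 19 requires contraception or abstinence in women of childbearing potential "for the duration of the study and for at least 6 months after the last dose of study drug". Criterion 21 requires a barrier method in men with partners of childbearing potential "from the start of study drug administration through at least 6 months after the last dose of study drug". Section 7.3.10, directly before the notification rule, adopts these periods by reference: "see the corresponding inclusion criteria in Section 4.1".

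Four other places touch on pregnancy or late events:

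- Sections 7.3.2 and 7.3.9 run SAE reporting from consent to 30 days after the end of participation, which both gloss as the last dose. Section 7.3.2 counts spontaneous abortion, stillbirth, neonatal death and congenital anomaly as SAEs.
- Section 7.3.5 keeps a later route open for "any untoward event that occurs subsequent to the AE reporting period that the investigator assesses as possibly related to the investigational drug/product".
- Table 6 in Section 7.3.8 asks for exposure to study drug during pregnancy to be reported, and gives no window for a conception after dosing has ended.
- SAP Section 6.6 says that pregnancy information will be listed.

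**The concern.** The protocol asks both sexes to avoid conception for six months after the last dose, yet the notification duty in 7.3.11 appears to lapse after the first 30 days. Pregnancies in the rest of that period are among those the precaution is meant to prevent.

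At stake is safety information. Section 1.2 describes unesbulin as destabilizing tubulin polymerization and DTIC as an alkylating agent. A pregnancy that is never notified produces no outcome form, so its outcome may not be learned, and the SAP listing can show only what was collected. Partner pregnancies are the least likely to come to light unless someone asks.

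**Working it through.** No power, alpha or sample-size figure is involved. The check is a comparison of windows plus one subtraction.

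**1. The windows side by side, counted from the last dose**

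| Place (Protocol) | What it governs | Runs until |
|---|---|---|
| 4.1, criterion 19 | Contraception, female subjects | at least 6 months |
| 4.1, criterion 21 | Contraception, male subjects with partners of childbearing potential | at least 6 months |
| 7.3.11 | Notification, subjects and partners | on study, or 30 days |
| 7.3.2, 7.3.9 | SAE reporting | 30 days |

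**2. Size of the gap.** Let L be the length of six calendar months, 181 to 184 days depending on the start month. Then uncovered days = L − 30, and uncovered share = (L − 30)/L.

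- L = 181: 181 − 30 = 151 days; 151/181 = 0.834
- L = 184: 184 − 30 = 154 days; 154/184 = 0.837

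The gap is 151 to 154 days, about 83% to 84% of the minimum contraception period.

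**3. Does another current section close it?**

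- *SAE reporting.* An outcome cannot precede its conception. Every outcome of a pregnancy that begins after day 30 therefore falls after the 30-day SAE window.
- *Section 7.3.5.* This needs an untoward event and a judgement that it is possibly related. An uncomplicated pregnancy meets neither condition. Section 7.3.1 defines an AE in terms of a study subject given study drug, so the reach of this route to a partner is not stated.
- *Table 6.* This concerns exposure during pregnancy and does not set a post-dose period for later conceptions.
- *SAP 6.6.* A listing does not create a duty to collect.

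None extends notification to six months.

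**4. What 'on study' could mean in 7.3.11**

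- *Reading A, on study ends with dosing.* The uncovered period is 151 to 154 days for everyone.
- *Reading B, on study includes survival follow-up.* The uncovered period is zero while a subject stays in follow-up. It is still 151 to 154 days for someone who leaves the study when dosing stops. I assume here that a partner is covered according to the male subject's status; the text does not say.

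Reading A is the more natural. Under B the 30-day limb would be left with little to do, and the SAE sections equate the end of participation with the last dose. Reading B cannot be excluded: Section 6.1.2 separates stopping study drug from leaving the study, Section 7.1 continues survival calls every 3 months, and Section 3.4 ends the study at the last subject's last visit.

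**The case against.** The strongest reply is that the rules do not conflict. Criteria 19 and 21 govern what subjects do, 7.3.11 governs what sites report, and a site can comply with both. That stands. A reader might infer that the windows contradict each other; the documents show only that they are not aligned.

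Second, a reader might infer that pregnancies after day 30 go unreported. That is too strong. Under Reading B many would be notifiable, and 7.3.5 still catches late untoward events judged possibly related. What the text supports is that notification is not required on the natural reading and not clearly required on any reading.

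Third, 83% might be taken as the share of risk or of pregnancies missed. It is neither. The documents give no expected number of pregnancies and no hazard by time since last dose, and no section calls the contraception period a measured risk period. The population has unresectable or metastatic disease, and women surgically sterilized, for example by hysterectomy, are not counted as of childbearing potential. The yield may be very small.

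Fourth, the amendment history for Version 3.0 mentions an update to pregnancy reporting alongside the move to six months. A reader might infer that the sponsor meant 7.3.11 to say six months. A change log cannot establish that, and this point rests on current text only.

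Fifth, SAP Section 3.5 records that the Data Monitoring Committee recommended stopping for futility, so few subjects may be affected by a change. That limits the reach. It does not remove the point, because the six months run from each subject's own last dose and so continue after treatment stops. The Study Manual, to which 7.3.11 refers for form details, is not among the documents and may say more.

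**Conclusion.** The point holds as a misalignment in safety reporting and is worth correcting. On the natural reading of 7.3.11, pregnancies in subjects or partners that begin from day 31 to month 6 after the last dose need not be notified, although the protocol requires contraception throughout that time. This rests on taking 'on study' to end with dosing and on six months as the minimum contraception period. If 'on study' was meant to include survival follow-up, the gap shrinks to those who leave the study, and the defect is then an undefined term that sites can apply in different ways. Either way the text needs attention. The number of pregnancies concerned cannot be derived from the documents. No endpoint, estimand, power or alpha figure is affected.

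**What to change.** Reconcile Section 7.3.11 with criteria 19 and 21 in Section 4.1 and the Synopsis, so that the notification window is no shorter than the post-dose contraception period the protocol sets, for subjects and for partners. Define 'on study' in 7.3.11, stating whether survival follow-up counts and how the term applies to a partner. This is a change to reporting only and takes no view on how long contraception should last.

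The cost is small but more than one line of text. Table 1 assigns only survival to the survival follow-up calls; AE collection ends with the earlier safety call. A pregnancy question would have to be added to calls already planned every 3 months after the end-of-treatment visit. The second of these falls around or after the end of the six months, so no new contact is needed for subjects who remain in follow-up. The pregnancy form instructions would have to match. For partners, the written consent that 7.3.11 already requires would apply to the added cases. Subjects who withdraw from the study altogether could still be missed.
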